## **Hypothesis**

Patients with ESKD as a result of CKD progression have sufficient RKF such that an initial dialysis regimen of twice-weekly HD plus adjunctive pharmacologic therapy (loop diuretics, potassium-binding agent, and sodium bicarbonate) will afford adequate solute and volume control.

Compared to the conventional HD regimen, a gradual HD regimen with supportive pharmacologic therapy will confer better preservation of RKF.

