## **Methods and Measures**

### **Design**

This randomized pilot trial will be parallel-arm in design. We will enroll 50 patients of age  $\geq 18$  years, with incident ESKD. Participants will be equally randomized to one of the two regimens: a) twice-weekly HD plus adjunctive pharmacologic therapy (loop diuretic, potassium-binding agent, and sodium bicarbonate) for six consecutive weeks, continued by thrice-weekly HD (intervention group); or b) thrice-weekly HD (comparator group) (Appendix A). Patients will be followed for 12 months after the date of randomization; or until transplant, death, withdrawal of consent, or transfer of care outside Wake Forest healthcare system, whichever occurs sooner. Feedback from the participants will be obtained during the study to (1) evaluate the delivery of study-related information, (2) evaluate coordination of care during the study as it pertained to study-related procedures, (3) evaluate patient perceptions on study-related assessments, (4) elicit patients' motivations for study participation, and (5) obtain participant input regarding future research concerning the study intervention.

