### **Sample Size**

The primary purpose of this pilot study is to evaluate the feasibility of a randomized intervention between a stepped regimen of HD and a standard regimen of HD. Therefore, for the primary feasibility outcome, we elect a pilot trial sample size of 50 patients total (25 patients per treatment group) which is consistent with recommendations for pilot and feasibility studies where samples of 10 to 20 participants per group have been deemed adequate to assess feasibility outcomes (Stat Methods Med Res 2016, 25(3), pp. 1057-1073). Power calculations for a future multicenter clinical trial will be carried out using the effect size on RKF and variability collected during this pilot study.

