### **Data collection**

Sociodemographic (age, sex, race, marital status, educational level, living arrangement) and clinical (ESKD etiology and comorbidities) data will be collected from all participants at enrollment, using direct patient interview and electronic medical records. Assessments of health-related quality of life (using Dialysis Symptom Index questionnaire), depression (using PHQ-9 questionnaire) and anxiety (using GAD-7 questionnaire) will be performed at enrollment and at week 6 and week 12 (month 3).

Laboratory data to include serum sodium, potassium, bicarbonate, phosphorus, calcium, intact PTH, albumin, hemoglobin, ferritin, transferrin saturation and beta-2 microglobulin will be recorded at baseline and then at set intervals according to the schedule of assessments (Appendix C).

A 24-hour urine collection will be performed at baseline (within 1 week prior to initiation of HD or within 1 week after initiation of HD). Inter-dialytic urine collection (starting with the end of one HD session and ending with the beginning of the next successive HD session) will be performed at set intervals during the study (weeks 6, 12 [month 3], 24 [month 6] and 48 [month 12] +/- 7 days). Measurements performed on urine collections will include urine volume, beta-2 microglobulin, urea and creatinine; these measurements will be used to calculate RKF (urea and creatinine clearance) and middle-molecule (beta-2 microglobulin) clearance.

Assessments of dialysis clearance using single pool Kt/V (spKt/V) and standard Kt/V (std Kt/V) will be performed according to standard of care.

Treatment with adjuvant therapy (e.g., Patiromer, Furosemide, Sodium Bicarbonate), intravenous iron, erythropoietin stimulating agent, active vitamin D and calcimimetic will be recorded as average weekly dose during weeks 0 to 6, and average weekly dose during weeks 7 to 12 (month 3). Prescription of renin-angiotensin inhibitors, beta blockers, antiplatelet therapy and/or lipid lowering medications will be recorded.

Study-specific assessments and measurements will include the Dialysis Symptom Index performed at 12 weeks (month 3), PHQ-9, GAD-7, urine collection and urine-based assays, serum measurement of beta-2 microglobulin, and serum K measurement at week 2 and 4 (Appendix C, Schedule of Assessments). Of note, baseline Dialysis Symptom, serum K measurement at week 1 and week 6, and all other aforementioned blood tests are part of standard of care.

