For evaluation of primary safety end points and secondary clinical end points, intention-to-treat principles will be followed. Evaluation of categorical end points will be performed using chi-squared tests. Evaluation of continuous end points will be performed using Student's unpaired t-test for normally distributed variables, or the Wilcoxon rank-sum test for nonparametric data. For comparison of variables measured during the time course of the study, a repeated measures analysis of variance (ANOVA) will be used. The consistency of effects on the primary end point will be explored in a variety of subgroups. Kaplan–Meier methods will be used for time-to-first hospitalization analyses. Missing RKF data for subjects will be replaced (rather than excluding them from the analysis, as missing RKF measurements might not be completely at random) using linear regression to estimate values based on other measurements for each subject (linear trend at point, SPSS). For each group-sequential analysis, the upper bound of the one-sided confidence interval for the hazard ratio (incremental HD to conventional HD) would be calculated with the use of the critical value from the Lan–DeMets–O'Brien–Fleming alpha-spending function, which preserves an overall one-sided alpha of 0.025. No adjustments for multiplicity will be made. An independent Safety Monitoring Committee will review all available data on a quarterly basis. Analyses that signal safety concerns (i.e., higher rates of hospitalization, treatment failure or death in the intervention arm compared to the comparator arm) will be reported to an independent Steering Committee to determine whether the study should be discontinued, be modified and then proceed, or continue with caution.

Descriptive statistics will be used to report the results of Participant Feedback Questionnaire.

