### **Data and Safety Monitoring**

Participants in the intervention arm will have more frequent analysis of their clinical status and lab results. These evaluations will be done at a minimum frequency of once per week in the intervention arms, versus twice per month in the comparator arm according to standard of care. The study team members (principal investigator and co-investigators) will be responsible for the frequent analysis of the participants enrolled in the intervention arm. Participants enrolled in the comparator arm will be evaluated according to the standard of care by their nephrologist. The principal investigator will be responsible for the overall monitoring of the data and safety of study participants. The principal investigator will be assisted by other members of the study staff.

Events related to the type of HD regimen--such as admission for volume overload or hyperkalemia in the incremental HD arm--will be closely tracked. Events will be recorded electronically and reported to the principal investigator monthly. An independent Safety Officer, unblinded to treatment assignments, will review, on a quarterly basis, all events of hospitalizations and cause of hospitalization, within the study cohort. All concerns regarding the frequency of HD will be reported to the Wake Forest IRB. In addition, the principal investigator, Safety Officer, and members of the research group will carefully consider amendments (including halting the trial if necessary).

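### Filling each missing RKF value with one straight-line prediction, with no uncertainty step or sensitivity analysis, can distort the RKF difference and SD in either direction

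*Combined protocol and SAP*

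**What the plan says.** The Analytical Plan fills missing RKF values "using linear regression to estimate values based on other measurements for each subject (linear trend at point, SPSS". The reason given for filling rather than excluding is "as missing RKF measurements might not be completely at random". The same section lists t-tests, Wilcoxon tests and, for repeated measurements, this: "For comparison of variables measured during the time course of the study, a repeated measures analysis of variance (ANOVA) will be used". It mentions no multiple imputation, variance correction or sensitivity analysis, and neither does any other section.

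RKF is measured at baseline and at "weeks 6, 12 [month 3], 24 [month 6] and 48 [month 12] +/- 7 days" (Data collection). Follow-up runs for 12 months "or until transplant, death, withdrawal of consent, or transfer of care outside Wake Forest healthcare system, whichever occurs sooner" (Design). The plan does not say whether visits after these events count as missing and are filled.

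The Hypothesis section states that "a gradual HD regimen with supportive pharmacologic therapy will confer better preservation of RKF". Under Sample Size, power calculations for a multicenter trial "will be carried out using the effect size on RKF and variability collected during this pilot study". That sentence names no time point and does not say whether filled values are included.

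**The concern.** A line through a patient's own visits yields one fixed value per gap. The later tests count it as an observation, so its error is never carried into the standard error. The method also does not meet its stated purpose: if a value is missing because of what it would have been, the patient's other visits do not reveal that.

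The visit pattern adds to this. By plan the HD schedules differ only in the first six weeks (Interventions and Interactions), so an early arm difference that then stays constant is plausible. A line through the early visits projects it forward as if it kept growing. RKF decline may also be curved, and a line extrapolated to week 48 then misses the true value.

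At stake are the RKF comparison, which addresses the second hypothesis, and possibly the effect and SD used to size the main trial.

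**Working it through.** **Inputs.** From the documents: visits at weeks 0, 6, 12, 24 and 48 (Data collection); 25 patients per arm (Sample Size); success if at least 80% adhere to timed urine collection (Primary feasibility outcome), so up to 20% non-adherence is tolerated. The documents give no RKF effect, SD, decline rate, measurement error or loss rate; all of these are assumed below. The plan's only sample-size figure is 2 × 25 = 50, a rule of thumb, so there is no power calculation to reproduce. The text does not say whether the line runs on weeks or on visit order. The named software function may settle it, but the documents cannot confirm this, so both are shown.

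**1. Weights of the line.** With k observed visits, the filled value is Σwᵢyᵢ, where wᵢ = 1/k + (x₀ − x̄)(xᵢ − x̄)/Sxx. To fill week 48 from weeks 0, 6, 12 and 24:

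- Weeks: x̄ = 10.5, Sxx = 315; weights −1.000, −0.286, 0.429, 1.857.
- Visit order (1 to 4, predicting 5): x̄ = 2.5, Sxx = 5; weights −0.5, 0, 0.5, 1.

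**2. What the filled value carries.**

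| Week 48 filled from four visits | Weeks | Visit order |
|---|---|---|
| Difference d by week 6, then constant | −0.286 + 0.429 + 1.857 = 2.0d | 0 + 0.5 + 1 = 1.5d |
| Difference growing as d × week/48 | 1.0d | 0.5 × 0.25 + 1 × 0.5 = 0.625d |
| Error variance, Σwᵢ², relative to one measurement | 1 + 0.08 + 0.18 + 3.45 = 4.7 | 0.25 + 0 + 0.25 + 1 = 1.5 |

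For a single gap at week 6, 12 or 24 with the other four visits observed, Σwᵢ² is 0.25-0.43.

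**3. Curved decline.** Assume 5 ml/min at baseline and a 20-week half-life. The values at weeks 0, 6, 12 and 24 are 5, 4.06, 3.30 and 2.18; the true week-48 value is 0.95. The week-scale line gives −5 − 1.16 + 1.41 + 4.04, about −0.70, which is impossible. With a 30-week half-life it gives 0.71 against a true 1.65. On visit order neither fill is negative.

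**4. Overall week-48 difference, 20% missing.** This is 0.8d + 0.2 × (filled difference).

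- Persisting: 0.8d + 0.2 × 2.0d = 1.20d on weeks; 0.8d + 0.2 × 1.5d = 1.10d on visit order.
- Growing: 1.00d on weeks; 0.8d + 0.2 × 0.625d = 0.925d on visit order.

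**5. Implied main-trial N, if filled data are used.** N ratio = (SD ratio)² ÷ (effect ratio)², for change to week 48. Assumed: baseline mean 5, SD 1.5 ml/min; linear decline of 0.05 (SD 0.025) per week, or exponential decline with median half-life 30 weeks (log-SD 0.4); measurement SD 0.3 or 0.8; d of 0.5 or 1.0; 20% missing completely at random, week 48 alone.

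| | Weeks | Visit order |
|---|---|---|
| Difference persists | 0.75-1.01 | 0.84-0.91 |
| Difference grows | 1.06-1.47 | 1.12-1.26 |

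For example, an SD inflated 1.04 times with an effect inflated 1.20 times gives 1.04²/1.20² = 0.75. True power against a planned 80% is Φ(2.8016√ratio − 1.96): 68% at 0.75 and 73% at 0.84.

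If the planning time point were week 12 or 24, the fill would be an interpolation. A separate simulation (exponential decline, measurement SD 0.6-1.5, 20-30% missing) found the SD of change 4-11% too small, which alone makes N about 8-20% too small.

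**6. Unequal loss, no true difference.** The spurious difference is (loss rate in intervention − loss rate in comparator) × mean error of a fill. Assume 2 of 25 lost in the intervention arm and 8 of 25 in the comparator arm, with week 48 or weeks 24 and 48 missing. On weeks, the intervention-minus-comparator difference is about +0.25 to +0.42 ml/min if decline is exponential and 0 if linear. On visit order it is about −0.12 to −0.29 ml/min. Type I error of a week-48 t-test is 0.050-0.103; with 5 of 25 lost in each arm it is 0.035-0.051.

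**7. Comparison with sampling error.** With complete data, a change SD of 1.27 or 1.65 (the linear-decline case) gives SE = SD × √(2/25) = 0.36 or 0.47. At d = 1, one SE upward makes N 1/1.36² = 0.54 or 1/1.47² = 0.46 times the right value. One SE downward makes it 1/0.64² = 2.4 or 1/0.533² = 3.5 times.

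**The case against.** The strongest reply is that the harm to the main trial is inferred. A reader might conclude that the filled values will set its size. Sample Size does not say so: it speaks of what the pilot collects, which can mean observed data only. This stands, and the N ratios are conditional on it. The ratios in step 5's table also apply to week 48, which the plan does not name as the planning time point.

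A reader might also conclude that the method favours the intervention, always shrinks the SD or generally inflates type I error. None of these follows. The SD shrinks for interior gaps and usually grows for an extrapolated week 48. The sign under unequal loss depends on the time scale, and equal random loss showed no inflation. Larger multipliers arise if week 24 is missing too (4.17d on weeks, 2.17d on visit order), but the documents do not show how often that would happen.

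It is tempting to expect unequal loss because clinical status and laboratory results are reviewed "at a minimum frequency of once per week in the intervention arms, versus twice per month in the comparator arm". That is weak support: urine collections follow one schedule in both arms. The 8-against-2 split is an assumption. The Analytical Plan also already reports drop-out by arm, so that need not be requested.

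Finally, RKF is a secondary outcome in a 50-patient feasibility pilot, and sampling error moves N more than most of the effects above. This limits the priority, but a confidence interval shows sampling error, whereas it does not show distortion from the fill.

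**Conclusion.** The point holds in limited form. The plan specifies a single deterministic fill, treats it as data, and tests no departure from its assumption despite doubting that loss is completely at random. The resulting RKF difference and SD can be wrong in either direction.

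The line multipliers and error variances are exact for the stated visits. The N ratios (0.75-1.47 on weeks, 0.84-1.26 on visit order) rest on assumed RKF inputs, 20% loss at week 48 alone, and use of filled data for planning. The 20% matches what the urine-collection criterion would tolerate, but that criterion does not say which visits are lost. The feasibility and safety outcomes are unaffected. The plan should be changed, but this is not a reason to hold up the trial.

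**What to change.** Drop the line imputation and make these changes in the Analytical Plan:

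- Analyse all observed RKF values with a REML mixed model. Include baseline as an outcome visit, so that patients with a missing baseline are kept. Use categorical visit, arm-by-visit terms with a common baseline mean, and vascular-access stratum.
- Use Kenward-Roger degrees of freedom and an unstructured covariance, with compound symmetry if it does not converge.
- Fill in no values after death, transplant, withdrawal or transfer.
- Name the time point whose effect and SD feed the main trial, take both from this model, and report them with confidence intervals.
- Add one not-at-random sensitivity analysis: delta-adjusted multiple imputation over a pre-specified range of deltas.

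The cost is plan wording, standard software and slightly more analysis work; no new data are needed. Convergence may be difficult with 25 per arm, and intervals may be wider. The fix does not reduce the sampling error of a pilot this size.

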### ***Primary safety outcomes***

Time point: end of month 3

The intervention of stepwise HD schedule will be considered safe, relative to standard HD schedule, if there will be no significant difference in severe adverse events between the two HD treatment groups during the first 3 months of the study.

Severe adverse event(s) will be defined as the requirement of one or more additional HD treatment(s) or hospitalization(s) for: (1) a condition related to poor volume control (i.e., clinically-determined volume overload, decompensated heart failure, or hypertensive urgency/emergency); (2) severe electrolyte imbalance (i.e., serum potassium  $>6.5\text{mEq/L}$ ); (3) severe metabolic acidosis (i.e., serum bicarbonate  $<15\text{mEq/L}$ ); (4) symptomatic uremia (i.e., uremic encephalopathy, uremic pericarditis); or (5) death associated with study intervention.

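### Does the group-sequential hazard-ratio bound need a named event, margin, maximum and consequence before this pilot can go ahead?

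*Combined protocol and SAP*

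**What the plan says.** The Analytical Plan states that at each group-sequential analysis "the upper bound of the one-sided confidence interval for the hazard ratio (incremental HD to conventional HD) would be calculated", with a critical value from the Lan–DeMets–O'Brien–Fleming spending function, "which preserves an overall one-sided alpha of 0.025". Two other sentences in that section bear on it. Kaplan–Meier "methods will be used for time-to-first hospitalization analyses", which makes first hospitalization the nearest candidate for the hazard-ratio event, though the plan does not say so. And "An independent Safety Monitoring Committee will review all available data on a quarterly basis", which suggests when looks might occur without calling those reviews the group-sequential analyses.

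The plan's decisions are stated separately:

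- **Progression to a main trial** rests on four feasibility proportions (Primary feasibility outcome; Analytical Plan).
- **Safety at month 3:** the stepped schedule is called safe "if there will be no significant difference in severe adverse events between the two HD treatment groups" (Primary safety outcomes).
- **Referral during the trial:** analyses that signal concern, explained as "higher rates of hospitalization, treatment failure or death in the intervention arm compared to the comparator arm", go to an independent Steering Committee "to determine whether the study should be discontinued, be modified and then proceed, or continue with caution".

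On duration, the Design section says: "Patients will be followed for 12 months after the date of randomization". The text supplied gives no recruitment period. The sample size is 50 patients, 25 per arm.

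**The concern.** A spending function turns an information fraction into a critical value, and the fraction needs a denominator: a maximum number of events or a total calendar duration. Neither is given, and the event is not named. The bound also has no stated null value. An upper limit on incremental versus conventional HD cannot show that incremental HD has the higher rate. It can exclude a chosen excess, which needs a margin, or show benefit if it falls below 1.

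The Human Subjects Protection section rates the study as high risk, and this is the plan's only formal sequential statement. A board could take the 0.025 as protection on the quarterly safety looks when no rule is explicitly attached to it. If a stopping or safety decision did depend on the bound, two competent analysts could get very different answers from the same interim data.

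**Working it through.** **Inputs from the plan:** one-sided alpha 0.025; O'Brien–Fleming-type spending; 1:1 allocation; 50 patients, so at most 50 first events. **Assumed, because the plan gives none:** event counts, maximum information, study duration and number of looks.

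**1. The plan's own figure.** The spending function is α(t) = 2[1 − Φ(z/√t)], where z is the upper 0.0125 normal quantile, 2.241. At t = 1, α(1) = 2 × 0.0125 = 0.025. The stated total is reproduced, by construction of the function.

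**2. How far an interim bound depends on the unstated maximum.** With 1:1 allocation and d events, the standard error of the log hazard ratio is about 2/√d. At an observed hazard ratio of 1.0 the upper bound is therefore exp(2c/√d), with c the critical value. For a first look at d = 12:

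| Assumed maximum | t | α(t) | c | Upper bound |
|---|---|---|---|---|
| 16 events | 0.75 | 0.00965 | 2.340 | 3.86 |
| 25 events | 0.48 | 0.00122 | 3.032 | 5.76 |
| 50 events | 0.24 | 0.0000048 | 4.428 | 12.89 |

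Spending on calendar time does not remove the dependence. A first look at month 9 with 12 events gives 5.53, 7.45 or 12.20 for an assumed study length of 18, 24 or 36 months (t = 0.50, 0.375, 0.25; c = 2.963, 3.479, 4.333).

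**3. The final look.** All remaining alpha is spent at the end, so the maximum drops out. Recursive integration with equally spaced looks gives a final c of 1.960, 1.969, 2.014 and 2.066 for 1, 2, 4 and 8 looks. The spread in step 2 is an interim matter only.

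**4. What a completed specification would deliver.** At the last of four equal looks (c = 2.014) and an observed hazard ratio of 1.0:

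- d = 8: exp(2 × 2.014/√8) = 4.15
- d = 25: exp(2 × 2.014/5) = 2.24
- d = 50: exp(2 × 2.014/√50) = 1.77

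For scale, take a fixed design with one-sided 0.025, 80% power and a true hazard ratio of 1. The events needed to exclude a margin m are 4(1.960 + 0.842)²/(ln m)². That is 66 events for m = 2.0, 191 for 1.5 and 457 for 1.3, all above the ceiling of 50. For the bound to fall below 1 with 50 events, the observed hazard ratio would have to be under 1/1.77 = 0.57.

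**5. Which rule does the interim safety work.** The stated trigger is higher rates in the intervention arm. Take it literally as any numerical excess of events at any of four looks, with a fixed probability p that each event falls in the intervention arm. Exact recursion gives:

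| Total events (looks at) | Referral if no difference, p = 1/2 | Referral if rates are 2:1, p = 2/3 |
|---|---|---|
| 25 (6, 12, 19, 25) | 0.66 | 0.98 |
| 8 (2, 4, 6, 8) | 0.51 | 0.82 |

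The trigger is sensitive and often false. That is tolerable because referral leads to deliberation, not to an automatic stop. It works without the hazard-ratio bound.

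**The case for a change.** The strongest case for acting is that the sentence claims error control in a trial that calls itself high risk, while nothing in the text lets a reader compute the interim bound or see what follows from it. Lan–DeMets spending frees the plan from fixing the looks in advance, but not from fixing an information scale. The Steering Committee is not clearly the bound's consequence, because its trigger is higher rates, which an upper limit cannot demonstrate. A wording edit would be cheap.

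The description of the gap stands. Three stronger statements do not. First, the bound is not limited to excluding harm against a margin: below 1 it would show benefit with no margin, although the null value is still unstated. Second, the critical value is not undetermined throughout: step 3 shows that the final one hardly moves. Third, it goes too far to say that the 0.025 governs nothing. The referral sentence concerns analyses that signal safety concerns, and the group-sequential analysis is described shortly before it in the same paragraph. The fair statement is that the link is not explicit.

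It could also be said that oversight is described twice. The Analytical Plan has a Safety Monitoring Committee and a Steering Committee. Data and Safety Monitoring has a Safety Officer, IRB reporting, and a group including the principal investigator that would consider halting. How these relate is not spelled out, but they can coexist. The Safety Officer's list covers hospitalizations only, but the committee's remit is all available data.

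**Conclusion.** The detail is missing, but nothing in the plan turns on it. The four feasibility proportions, the month-3 safety comparison and the higher-rates referral all stand whether the sentence is completed, deleted or left alone. Participants are protected by at least weekly review in the intervention arm, monthly event reports, quarterly independent review and the freedom to change HD frequency at any time.

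Filling the gap would buy very little. With the information a 50-patient pilot can yield, the final upper bound at an observed hazard ratio of 1.0 is between about 1.8 (50 events) and 4.2 (8 events). An analyst can sensibly apply the calculation to first hospitalization, the one end point with a time-to-event method, and report it as supportive. Statisticians could differ on whether to complete the sentence or drop it, and neither choice improves a conclusion. The interim 0.025 should be read as unspecified, neither as a guarantee nor as a demonstrated failure.

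This rests on assumed event counts, looks and durations, and on the text supplied: the appendices are listed but not reproduced. It would be different if a stopping rule or safety claim were made to depend on the bound. No change to the plan follows.
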